2.3.1 Risk Assessment

Based on the clinical data available for RNS60 to date, the major possible risk for the proposed use is:

- Circulatory volume expansion/fluid volume overload

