6.8 Rescue Medicine/Treatment

6.8.1 Early Study Drug Cessation

The intervention is 0.5 mL/kg/h RNS60 (up to a maximum of 65 mL/h) and 1 mL/kg/h RNS60 (up to a maximum of 130 mL/h) intravenous infusion using an infusion pump, starting after randomization to a participant undergoing endovascular mechanical thrombolysis/thrombectomy. It is expected that infusion will begin prior to the completion of the procedure (defined as the time of arterial access closure) and complete 48h after the infusion is initiated.

The infusion may be stopped if the treating investigator believes the volume of infusion can no longer be tolerated due to volume overload (worsening dyspnea, hypoxia, or cardiac function). As such, the investigator may terminate drug administration at his/her discretion.

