2.2.4 Sample Size Determination

As the primary aim of this proof-of-concept study is to demonstrate safety, no power analysis was conducted for sample size determination. The trial targets to enroll a total number of 100 participants aged 18 years or older with LVO AIS and who are selected for endovascular revascularization.

Anticipated attrition factors include death from stroke unrelated to treatment (10%), discontinuation of treatment due to symptoms of fluid overload (20%), and early discharge (5%).

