3.5 Safety Assessment

Safety data will be summarized by actual treatment received and in total based on the Safety Population.

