3.5.1 Adverse Events (AEs)

An AE is defined as any untoward medical occurrence in a subject or clinical investigation participant administered a pharmaceutical product and which does not necessarily have to have a causal relationship with this treatment.

An AE can therefore be any unfavorable and unintended sign (including an abnormal laboratory finding, for example), symptom or disease temporally associated with the use of a medicinal product, whether or not considered related to the medicinal product. AEs will be captured from the start of study drug infusion through study completion (Day 90). All AEs will be coded to system organ class and preferred term using MedDRA version 24.0. A medical review of the coding reports will be performed prior to database lock. Treatment-emergent adverse events (TEAEs) are defined as AEs that start after the study drug infusion.

The investigator will grade the intensity of the AE as mild, moderate, or severe.

The relationship of an AE to study drug will be assessed as related, possibly related, or unrelated.

An overview of AEs will be provided including counts and percentages of subjects (and event counts) with the following:

- Any TEAEs (overall and by maximum severity)
- Any study drug related TEAEs (overall and by maximum severity)
- Any SAEs
- Any treatment-emergent serious AEs (TESAEs)
- Any study drug related TESAEs
- Any TEAEs leading to discontinuation of study drug infusion
- Any AEs leading to death
- TEAE occurrence by Month (Day 0-Day 7, Day 8 – Day 14, Day 15 – Day 21, Day 22 – Day 30, Day 31-Day 60, and Day 61-Day 90)

Counts and percentages of subjects (and event counts) will also be presented by system organ class and preferred term for each of the categories in the overview. If more than one event occurs with the same preferred term for the same subject, the subject will be counted only once for that preferred term using the most severe occurrence for the summary by severity. The number of events will be presented for overall category of TEAE and for each system organ class and preferred term. The number of events will not be presented for each category of maximum severity. AE listings will include the following information:

- Subject ID
- Adverse event term
- Adverse event preferred term
- System Organ Class
- Start date
- Outcome
- End date
- Relationship to study drug
- Action taken with study drug

- Severity
- SAE Criteria

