AEs with missing start dates will be considered as treatment-emergent. The first date of the month will be used to impute missing start days and January will be used to impute missing start months.

Listings will be presented specifically for SAEs and TEAEs leading to discontinuation of study drug.

3.5.2 *Clinical Laboratory Tests*

Blood for clinical laboratory tests will be collected at baseline and Day 2 and processed by the local laboratory. A list of laboratory tests to be performed and their standard units is included in Appendix A. Normal range files for local laboratories used in the study are provided by each site one time prior to database lock.

Absolute values and changes from baseline in standard unit will be summarized descriptively. The incidence of abnormalities (as defined by normal ranges) and clinical significances prior to the study drug infusion and after the study drug infusion will be summarized with counts and percentages of subjects.

3.5.3 *Vital Signs*

Blood pressure and heart rate will be measured at baseline, and per routine site standard of care, every 8-12 hours during Day 1 and Day 2 until completion of the infusion. Temperature will be recorded at baseline only if collected as standard of care. Since blood pressure and heart rate are measured every 8 hours during Day 1 and Day 2, the timepoints for the descriptive summarization of blood pressure and heart rate will be derived as follows:

Table 6: Vital Signs Timepoints derivation

| Derived Timepoint | Assessment Performed |
|-------------------|-----------------------------------|
| Hour 8 | After baseline and up to 12 hours |
| Hour 16 | 13 hours to 20 hours |
| Hour 24 | 21 hours to 32 hours |
| Hour 36 | 33 hours to 42 hours |
| Hour 48 | 43 hours and beyond |

Absolute values and change from baseline through the end of drug infusion of BP, heart rate, and temperature will be summarized using descriptive statistics by treatment group and time point. The number of available observations and out-of-range values (see Table 7) will be presented by treatment group and time point. Vital sign variables will be listed. Hypotension and hypertension thresholds are site dependent and evaluated by the investigator based on the individual's medical history and current status.

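### No planned table counts, once per patient and by arm, those with fluid overload, the one major risk the protocol names

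*SAP*

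**What the plan says.** **The risk.** Protocol 2.3.1 lists a single item: "Circulatory volume expansion/fluid volume overload". SAP 2.2.4 and Protocol 9.1 anticipate 20% attrition from it, for all arms together. Protocol 6.8.1 allows the infusion to be stopped if the investigator believes that "the volume of infusion can no longer be tolerated due to volume overload (worsening dyspnea, hypoxia, or cardiac function").

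**The data collected.** Protocol 5.5.5 requires examinations every 8 to 12 hours for signs of overload. Protocol Table 10-1 gives fluid monitoring as the purpose of the chest X-ray, and Protocol 8.1.2 makes any new abnormality on the 24 h or 48 h film an AE. Protocol 8.2.2 and 10.3.2 ask sites to record a diagnosis in preference to signs. Section 8.2.2 accepts signs when no single diagnosis can be made.

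**The planned display.** Under SAP 3.5, "Safety data will be summarized by actual treatment received and in total based on the Safety Population". SAP 3.5.1 gives overview categories, one of which is "Any TEAEs leading to discontinuation of study drug infusion". It then states: "Counts and percentages of subjects (and event counts) will also be presented by system organ class and preferred term for each of the categories". For repeated events, "the subject will be counted only once for that preferred term". It also says: "Listings will be presented specifically for SAEs and TEAEs leading to discontinuation of study drug".

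**Other sources.** SAP 3.5.6 lists chest X-ray results, although the protocol synopsis (Laboratory Tests) says they will be reported and analysed. SAP 3.5.5 grades examinations in three levels of abnormality, none specific to overload. SAP 3.3.7 counts patients with compliance below 80% by treatment. No section of the SAP defines an event of special interest, a grouped query or a composite overload variable.

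**The concern.** Overload can reach the AE database as a diagnosis, as breathlessness, as low oxygen, as a cardiac sign or as an X-ray finding. These may code to different preferred terms. The once-per-patient rule works inside one term, so a reader cannot add the rows to get patients, and the system organ class rows group by organ rather than by overload.

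A safety trial could then report its main expected harm only in pieces. Someone can rebuild the count from listings, but would be choosing the terms after the arms are known. The design makes a by-arm count useful as well: placebo and high dose receive the same volume and low dose half of it, so a pure volume effect would not appear in high dose against placebo.

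**Working it through.** The plan gives no derivation for the 20% and no power analysis, so there is no stated figure to reproduce. The check asks what the planned rows can and cannot show.

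**1. Inputs.** Target 100 patients at 1:1:1, so 100/3 = 33.3, taken as 33 per arm. Stops for overload symptoms: 20%, taken as equal across arms (assumption).

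**2. Expected size.** 0.20 × 100 = 20 patients in total; 0.20 × 33 = 6.6, about 7 per arm. 7/33 = 21.2%, Clopper-Pearson 95% CI 9.0% to 38.9%.

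**3. Why rows do not add.** Suppose one arm shows three sign-related rows with 3, 2 and 2 patients (assumed). The number of distinct patients lies between the largest row and the sum:
- full overlap: 3/33 = 9.1% (95% CI 1.9% to 24.3%);
- no overlap: (3 + 2 + 2)/33 = 7/33 = 21.2% (9.0% to 38.9%).

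The planned tables cannot tell these apart. If every case is coded to one diagnosis term, the row equals the patient count and nothing is lost.

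**4. What bounds the stops.**
- Lower bound: the overload diagnosis row within the discontinuation category. If a share s is coded only to signs, it shows 20 × (1 − s): 20, 15 or 10 patients for s = 0, 0.25 or 0.50. The range of s is assumed; the documents give no value.
- Upper bound: the any-cause discontinuation row, which counts patients across all terms. It contains all 20 if each stop is recorded through an AE.
- Second upper bound: compliance below 80%, which means under 0.80 × 48 = 38.4 h of infusion. It includes stops for other reasons and misses stops after 38.4 h.

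**5. What is not bounded.** A patient whose overload is treated while the infusion continues is in neither upper-bound row. If that case is recorded as signs or as an X-ray abnormality, it is not in the diagnosis row either.

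**6. The volume contrast.** 1 mL/kg/h × 48 h = 48 mL/kg for high dose and placebo; 0.5 × 48 = 24 mL/kg for low dose. At the rate caps, 130 × 48 = 6.24 L against 65 × 48 = 3.12 L. To gauge precision only, assume 13/33 in each full-volume arm and 7/33 in low dose. These rates exceed the 20% planning figure. The difference is 39.4% − 21.2% = 18.2 points, with Newcombe 95% CI:
- one full-volume arm vs low dose: −4.0 to 38.1;
- both full-volume arms (26/66) vs low dose: −1.6 to 34.2.

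Both include zero, so the grouped row is for estimation and not for testing.

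**The case against.** The best case for the plan concerns the stops. An infusion halted because the investigator judges the volume no longer tolerable has in effect been given a diagnosis, and Protocol 8.2.2 and 10.3.2 then ask for that diagnosis. Sign-only coding should be uncommon in this group, and the bounds in step 4 apply anyway. The dedicated listing of discontinuation events and the signs already named in Protocol 6.6 and 6.8.1 limit the freedom to choose terms later. SAP 3.5.3 also compares maximum blood-pressure deviation by arm, which bears on volume expansion. The DSMB charter and the programming specifications, which are not available here, may hold a definition.

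Most of this stands for patients who stop. It does not reach overload managed without stopping, where milder or ambiguous pictures make coding to signs or X-ray findings more plausible. Blood pressure is not a count of overload cases, and the SAP, which declares itself the governing document, contains no grouping.

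A reader might go further and infer that the tables will understate overload, or that a low diagnosis row would contradict the 20% planning figure. The documents support neither. The share coded to signs is unknown, and the 20% is an attrition assumption that the SAP never tests. At arm level even 4/33 = 12% has a 95% CI of 3% to 28%, which includes 20%. Nor would grouping make the rate independent of how sites describe events: a narrow list of diagnoses still rests on their wording.

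**Conclusion.** The gap is real and modest. As the SAP stands, the report will have no by-arm patient count for the single major risk named in the protocol. For stops, the planned rows bracket the answer, subject to the limits in step 4. For overload treated without stopping, no row isolates it.

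The understatement cannot be sized from the documents and is zero if sites consistently report the diagnosis. The primary endpoints, SAEs and 90-day mortality, do not depend on it. The conclusion rests on the SAP text alone; the equal 20% per arm, the coding shares and the example counts are assumptions used for illustration. This is a low-cost improvement to a descriptive display, not a flaw in the safety comparison.

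**What to change.** Before unblinding, fix a MedDRA term list and add to SAP 3.5.1 a grouped fluid-overload row that counts each patient once:
- **Narrow:** overload diagnoses.
- **Broad:** the narrow terms plus the dyspnea, hypoxia and cardiac-function signs of Protocol 6.6 and 6.8.1, and chest X-ray abnormalities reported as AEs.

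Require onset during infusion or within a stated short time after it ends. Report n/N by arm with exact 95% CIs, both overall and within TEAEs leading to discontinuation; only the latter is comparable with the 20% planning figure. Give differences with 95% CIs for each RNS60 dose against placebo, and for the two full-volume arms together against low dose. Label all of it descriptive.

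The cost is a paragraph in the SAP, a blinded review of a short term list (it can join the medical review of coding already planned before database lock) and one table from AEs already coded. No new data are needed.

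The downsides should be stated beside the table. The broad version takes in some events from other causes, such as pneumonia. The narrow version still depends on site wording. Precision at about 33 per arm is low. SAP 2.2.2 acknowledges that the slower rate may unblind infusion staff in the low-dose arm, which could affect reporting there.

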4 DATA SAFETY MONITORING BOARD

A Data Safety Monitoring Board (DSMB) will monitor the safety of subjects over the course of the study. The DSMB will meet at least twice during the subject enrollment period to examine the unblinded accumulated safety data. Subjects, investigators, site staff and in general all personnel directly involved in the conduct of the study will remain blinded to the subjects' treatment assignment until the completion of the study.

Details related to the DSMB responsibilities, authorities, and procedures will be performed in accordance with the DSMB charter.

5 CLINICAL MONITORING OF DATA

To ensure overall quality in data capture and recording, the study will have experienced monitors conduct both on-site and remote monitoring visits at every site at a frequency/duration based on the rate of enrollment, site assessments and needs, and/or identified risks. Each site investigator agrees to allow the monitor direct access to relevant records, and to be available upon request to discuss any issues and to resolve queries. Monitoring responsibilities and expectations are detailed in the Clinical Monitoring Plan.

6 ANALYSIS TIMING

6.1 Interim Analysis

No interim analysis is planned.

6.2 Pre-Final Analysis

After the database is locked and exclusions from analysis populations have been finalized, the randomized treatment assignments will be unblinded and the pre-final analysis will be generated. Pre-final Tables, Figures and Listings (TFLs) will be provided approximately 3 weeks after database lock.

6.3 Final Analysis

After all comments on the pre-final analysis have been resolved and the study database is declared final, the final analysis will be generated. Final TFLs will be provided approximately one week after the study database is declared final. If there were no changes to the pre-final analysis or the study database, the pre-final TFLs may be considered final. In addition to TFLs, study data tabulation model (SDTM) data and analysis data model (ADaM) data along with associated files will be provided. Associated files may include annotated CRFs, SDTM specifications, SDTM programs, ADaM specifications, ADaM programs, TFL programs, and clinical data interchange standards consortium (CDISC) Define packages for both SDTM and ADaM data.

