All participants, investigators, their clinical staff, local laboratories, study personnel, the data management group, and the sponsor staff and delegates will be blinded to the randomization codes and study drug assignment. All study personnel (Contract Research Organization (CRO) and Sponsor and sites) will remain blinded to this data until database lock, at minimum. In the event of emergency unblinding due to participant safety, the Investigator may request unblinding of that participant only. Processes and procedures for unblinding will be accordance with the study protocol, Data Management Plan, Safety Management Plan, and any applicable CRO or Sponsor Standard Operating Procedures.

2.2.3 *Study Drug*

RNS60 is [REDACTED]

[REDACTED] RNS60 has demonstrated exceptional safety in rodent and non-human primate toxicity studies. Additionally, RNS60 has demonstrated significant efficacy in a non-human primate model of acute ischemic stroke without any indications of adverse effects. In all clinical studies to date, RNS60 has been well tolerated. In this study, infusion will begin prior to the completion of the endovascular revascularization procedure (defined as the time of arterial access closure) and complete 48h after the infusion is initiated.

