3.4.4.3 Secondary Endpoints Analyses with Additional Covariates

The statistical models for one or more of the secondary endpoints may be amended to include additional covariates such as last known well time frame (≥ 6 hours or < 6 hours) and use of thrombolytics. This may be performed as post-hoc analyses.

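### SAP 6.2 and 6.3 lock the database and unblind, but declare the database final only after comments on the unblinded results, and state no control on data changes in between

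*SAP*

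**What the plan says.** SAP 6.2 (Pre-Final Analysis) makes unblinding conditional on two things: the database is locked, and exclusions from the analysis populations are settled. After that, "the randomized treatment assignments will be unblinded and the pre-final analysis will be generated". On timing, "Pre-final Tables, Figures and Listings (TFLs) will be provided approximately 3 weeks after database lock".

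SAP 6.3 (Final Analysis) then introduces a second database milestone, tied to the review of that output: "After all comments on the pre-final analysis have been resolved and the study database is declared final, the final analysis will be generated". On timing, "Final TFLs will be provided approximately one week after the study database is declared final". It adds: "If there were no changes to the pre-final analysis or the study database, the pre-final TFLs may be considered final".

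On blinding, SAP 2.2.2 (Randomization and Blinding) says that study personnel at the CRO, the sponsor and the sites "will remain blinded to this data until database lock, at minimum". Protocol 6.3.2 likewise places unblinding after database lock.

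**The concern.** A lock protects the analysis only if the data no longer change once the codes are open. Here the lock comes first, but final status is conferred later, after people have read and commented on results by arm. Questions raised about data at that stage may be selective, even in good faith: an unexpected or disappointing figure attracts scrutiny that a welcome one does not.

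What is at stake is the efficacy inference. SAP 3.4.2 ranks 15 comparisons in a fixed order to control the overall type I error, starting with dichotomised mRS at Day 90, high dose against placebo. A comparison that follows a non-significant one is read as exploratory. A change to one or two values at the first step can therefore decide how every later step is read. With arms this small, few changes are needed.

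**Working it through.** **Order of events.** The plan gives no figure to reproduce here, so the check is to set the sections side by side.

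1. Database locked, exclusions finalised (SAP 6.2).
2. Codes opened, pre-final analysis generated (SAP 6.2).
3. Pre-final tables, figures and listings at about lock + 3 weeks (SAP 6.2).
4. Comments raised and resolved; duration not stated (SAP 6.3).
5. Database declared final (SAP 6.3).
6. Final tables about 1 week after step 5 (SAP 6.3).

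The condition in 6.3 about there having been no changes has a purpose only if the analysis or the database can change between steps 3 and 5. The SAP's blinding guarantee for CRO, sponsor and site personnel in 2.2.2 is secure only up to step 1, so it does not cover this interval. SAP 4 keeps investigators and site staff blinded until completion of the study. However, Protocol 4.1 and SAP 2.2.1 define the end of the trial as the last participant's Day 90 visit or contact, which can come before lock. That protection may therefore already have ended.

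**How much a few recodes can do.** This is an unadjusted illustration, not the planned mixed model.

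Inputs:
- 100 patients randomised 1:1:1 (SAP 2.2.4 and 2.2.1), so 100/3 ≈ 33 per arm.
- Two-sided alpha 0.05 (SAP 3.4.2).
- The event counts are assumptions; the documents do not give them.

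One recoded patient moves an arm's proportion by 1/33 = 3.0 percentage points.

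The uncorrected chi-square is equivalent to z = (p2 − p1) / √[p(1 − p) × 2/33], where p is the pooled proportion.

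- 15/33 (45.5%) vs 21/33 (63.6%): p = 36/66 = 0.5455; z = 0.1818/0.1226 = 1.48; chi-square p = 0.138, Fisher p = 0.216.
- 13/33 (39.4%) vs 21/33 (63.6%): p = 34/66 = 0.5152; z = 0.2424/0.1230 = 1.97; chi-square p = 0.049, Fisher p = 0.084.

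Two recodes in one arm and in one direction thus cross 0.05 by chi-square but not by Fisher.

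Now take about half of placebo patients with mRS 0–2, an assumption guided by the background statement in Protocol 2.1. With placebo at 17/33:

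| Other arm | Chi-square p | Fisher p |
|---|---|---|
| 24/33 | 0.076 | 0.127 |
| 25/33 | 0.041 | 0.072 |
| 26/33 | 0.020 | 0.038 |

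One recode crosses 0.05 by chi-square between 24 and 25, and by Fisher between 25 and 26. Varying the placebo count gives the same pattern. For 13, 16 and 20 placebo responders, the chi-square crossing lies between 20 and 21, 23 and 24, and 27 and 28 in the other arm.

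**The case against.** The strongest defence is that this is a wording gap, not a plan to edit data. Much of it stands.

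- **The lock comes first.** A reader might infer that codes are opened on an open database. SAP 6.2 says the reverse: lock and final exclusions precede unblinding. SAP 3.2.4 also fixes per-protocol exclusions before unblinding, and SAP 1 has the SAP itself finalised before lock. These protect population membership and the written plan. They do not govern changes to data values after lock.
- **No permission is granted.** A reader might take 6.3 as authorising edits. It says only when a rerun is unnecessary. It implies that changes can occur and sets no rule for them.
- **Some judgement-based steps close before lock.** Medical review of adverse event coding (SAP 3.5.1) and calculation of infarct growth (Protocol 8.1.10) are both scheduled before lock, so neither is a good example of exposure.
- **Model changes.** A reader might link 6.3 to SAP 3.4.4.3, where "The statistical models for one or more of the secondary endpoints may be amended to include additional covariates". That section goes on to say that this may be done post hoc, the SAP version history labels it so, and nothing there refers to the pre-final review. It does not support the concern.
- **Site entry.** Protocol 10.3.3 takes the electronic data tool off-line once the study is completed at a site, which limits direct site edits. It still leaves a route for late serious adverse event reports and updates, and it does not cover changes made centrally.
- **Unseen documents.** An unlock procedure may exist in the Data Management Plan. SAP 2.2.2 names that plan for unblinding procedures, not for corrections after lock. The absence of a control is shown only for the protocol and SAP.
- **Purpose of the trial.** Safety is primary, there is no power analysis, and Protocol 9.3.3 presents the efficacy results as estimates for planning a later trial. This lowers the stakes. The SAP nonetheless claims type I error control for the efficacy hierarchy.

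**Conclusion.** The point holds in a limited form. The SAP places final status for the database after the unblinded results have been seen, foresees data changes in that interval, leaves its length open, and states no unlock control.

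A reader might infer that the type I error control is already lost. The documents do not support that: it is at risk only if data are edited with arm-level results known, and nothing says that they will be. The size shown, one or two patients to cross 0.05, applies to a result already near the boundary. It rests on about 33 per arm, assumed event counts, recodes in one direction within one arm, and unadjusted tests in place of the planned model.

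This should be fixed, but it is not a fault that invalidates the analysis by itself. Because the SAP declares itself the governing document (SAP 1 and 6.4), the control belongs there.

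**What to change.** Reorder SAP 6.2 and 6.3:

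1. Lock the database and finalise the population exclusions, as now.
2. Run the pre-final tables, figures and listings on dummy treatment codes.
3. Resolve all comments and declare the database final.
4. Release the real codes and run the final output.

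Add that any data correction after this needs a documented unlock: a stated reason, approval by people blinded to the results, an audit trail, and the lock-version and final results reported side by side.

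If the sponsor prefers to keep the present order, the same unlock rule applied from the 6.2 lock onward would close the main gap, though comments would still be made with results in view.

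The cost is SAP wording, one dry run on dummy codes and some scheduling between lock and code release. No new data are needed.
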